This is a single-center, prospective, ‘open-label,’ investigator-initiated pilot study evaluating the role of continuous glucose monitor (CGM) use either alone or with remote monitoring capabilities that enable subjects to share CGM data with family and friends (whom we will call “followers” in this protocol) among women with T1DM associated with pregnancy. We hypothesize that CGM use will decrease percentage of glucose values below the target range, decrease frequency of severe hypoglycemic episodes, and increase post-prandial glucose values into the target range, with a possible reduction in A1C compared to not using CGM during pregnancy. We hypothesize that the use of remote technology (**Share™ technology**) with subject’s designated follower will decrease hypoglycemia fear and the frequency of severe hypoglycemic episodes compared to CGM use alone in pregnancy or not using CGM use in pregnancy. This study aims to improve maternal glucose management among women with T1DM with a hope to also improve health outcomes during pregnancy.

The study will enroll up to 40 patients from the Barbara Davis Center for Childhood Diabetes (BDC) Adult clinic over the age of 18 years who are pregnant (13 weeks gestation or less) or plan to become pregnant within the following 6 months. The study will also attempt to enroll up to 40 followers (one per pregnant subject) who are family members or friends of the pregnant subjects and over the age of 18 years. All subjects meeting these criteria will be invited to sign informed consent and participate in the study. All pregnant subjects will be stratified into one of three groups: (1) CGM use alone, (2) CGM use with Share™, (3) no CGM use. CGM use will be offered to all subjects, but individuals who do not want to wear a CGM will be stratified to Group 3. Stratification for Groups 1 and 2 will depend on the following: subjects and followers who have iPhones, iPads, and/or iPod touches will be placed into Group 2 which requires one of these devices to function, while all others will be placed in Group 1. All subjects will be followed for study visits with similar frequency during the pregnancy, and subjects in Groups 1 and 2 will wear the Dexcom G4 Platinum® CGM system from the first pregnancy visit until delivery. All subjects in Group 2 will also use the Share™ technology from the first pregnancy visit until delivery.

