CGM data will be analyzed for mean blood glucose values, time spent in hyperglycemic (>240, >300mg/dl) and hypoglycemic (<50, <70, <80 mg/dl) ranges and various indices of glycemic variability. Laboratory analysis for A1C will be performed at baseline, monthly thereafter during the pregnancy, and post-partum. Routine blood tests will be performed in all subjects in each trimester (see Table 1).

Primary outcomes will be:

- 1) Glucose variability as measured by glucose excursions from self-monitoring blood glucose (SMBG) data through log books and downloads as well as CGM downloads and various indices [J-index, mean amplitude of glycemic excursion (MAGE), high blood glucose index (HBGI), low blood glucose index (LBGI)] from CGM downloads.
- 2) Changes detected by the hypoglycemia fear questionnaire.

Secondary outcomes will be:

- 1) How CGM alone and CGM with Share™ usage affect A1C compared to no CGM use,
- 2) Progression of diabetes complications (retinopathy, nephropathy),
- 3) Maternal and fetal outcomes (eclampsia/pre-eclampsia, live birth rates, birth weight, neonatal hypoglycemia, and other similar measures).

Introduction:

Among the US population, 29.1 million people (9.3%) have diabetes (1). Pre-existing diabetes has to be managed very carefully throughout pregnancy to optimize maternal and fetal outcomes (2). Among women

with T1DM who are pregnant, the tools that we have to regulate maternal glucose control include multiple daily injections (MDI), continuous subcutaneous insulin infusion therapy (CSII) also known as insulin pump therapy, and for high-risk individuals continuous glucose monitoring (CGM) (2). CGM use in pregnancy has been shown to be safe, to reduce the frequency of severe hypoglycemia, and to improve A1C values (3-6). Sensor-augmented pump therapy with CGM use continuously was shown to lower A1C more than intermittent use in pregnant women with T1DM (7). However, few studies have measured changes in glucose variability that occur with CGM use during pregnancy and no studies have evaluated how tools that allow family and friends (followers) to access glucose trends affect outcomes during pregnancy.

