The primary endpoints are glucose variability and changes detected by hypoglycemic fear survey. We will measure indices of glucose variability (mean glucose \pm SD, % of glucose within/above/below target ranges, J Index, High Blood Glucose Index [HBGI], Low Blood Glucose Index [LBGI], Mean Amplitude of Glycemic Excursions [MAGE], CONGA_n) throughout pregnancy using the SMBG 7-point profiles for one week taken once per trimester. Hypoglycemic fear survey results will be assessed once monthly over the pregnancy. We will compare outcomes within individuals over time and between individuals of the different study arms. We will test whether outcomes differ between women using Dexcom alone and women using Dexcom with Share™ using interaction terms, and will stratify analyses if differences by group are greater than 10 mg/dL in mean glucose levels are detected. Since SMBG logs will be taken at multiple time points over the pregnancy and since CGMs will be worn continuously for the duration of each pregnancy, linear mixed models will be used to assess changes in outcome measures (GV, time spent in target below or above target) over time in each trimester of pregnancy. We will use linear mixed models to assess changes in the hypoglycemic fear survey in each month of the pregnancy. Secondary endpoints include A1C differences among study arms. Improvement in glycemic variability parameters with a possible reduction of A1C by 0.3%, measured as the difference of the mean A1C laboratory values of the arms of the study between baseline (0-3 months, first trimester), second trimester (3-6 months), and third trimester (6 to 9 months). Mixed models account for missing data, allow for an unstructured covariance matrix for repeated measures, and account for inter-subjects correlation of measurements. Secondary outcomes will be used

in the same mixed models. Differences in frequency of low alert glucose rates, high alert glucose rates, and interventions for low or high glucose values among the followers for each study arm will be analyzed with student t-tests. A p-value < 0.05 will be considered significant, and we will perform statistical analyses with SAS software (version 9.3, SAS Institute, Cary NC).

Publication Strategy:

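### Two primary endpoints cover 9 or 10 glucose indices plus a fear survey, with p < 0.05 applied throughout and no deciding measure, contrast or time point, so the false-positive risk is about 18% to 93%, depending on how the plan is read

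*Combined protocol and SAP*

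**What the plan says.** The Statistical Analysis Plan states: "The primary endpoints are glucose variability and changes detected by hypoglycemic fear survey". It then lists the glucose measures. The list opens "We will measure indices of glucose variability (mean glucose" with its SD, and continues with the percentages "of glucose within/above/below target ranges, J Index, High Blood Glucose Index [HBGI], Low Blood Glucose Index [LBGI], Mean Amplitude of Glycemic Excursions [MAGE" and finally CONGA_n. The data are to be collected "throughout pregnancy using the SMBG 7-point profiles for one week taken once per trimester".

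On comparisons it says: "We will compare outcomes within individuals over time and between individuals of the different study arms". Group 1 and Group 2 are compared again through interaction terms, and analyses are stratified if mean glucose differs by more than 10 mg/dL. Linear mixed models assess glucose by trimester and fear by month. The only decision rule is "A p-value < 0.05 will be considered significant". No multiplicity adjustment, hierarchy or exploratory label appears.

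Other sections widen the choice:

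- The opening summary draws the primary glucose outcome from both SMBG and CGM. For CGM data it lists the "hypoglycemic (<50, <70, <80 mg/dl) ranges" plus two high cut-offs. The analysis plan gives no numeric target range.
- The summary begins its hypotheses with "We hypothesize that CGM use will decrease percentage of glucose values below the target range", but adds severe hypoglycemia, post-prandial glucose and possibly A1C for CGM. For Share it names fear and severe hypoglycemia, each against two comparators.
- Appendix C has a Behavior and a Worry section. No section says which score is analyzed.

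**The concern.** When a primary endpoint is a list and each entry can be tested in several ways, a 5% rule per test does not give a 5% risk for the endpoint. It is also unclear what result would support or refute either hypothesis, because no index, arm pair or period has been given that role. The measure, cut-off, contrast and trimester to headline could be picked after the data are seen.

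This matters for what follows. The Weakness of the Study section says the results will inform a much larger randomized study, and the Publication Strategy foresees conference presentations and possible journal papers. A chance finding could be reported as a primary result and shape the next trial's endpoint.

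**Working it through.** **Figure stated in the plan.** The only sample-size figure is 40 recruited with 20% drop-out: 40 x 0.80 = 32 completers, which reproduces. The plan states no power and no family-wise error rate, so there is none to reproduce.

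**Count of measures.** Mean and SD (2, or 1 if read as a single summary), percent within, above and below target (3), J Index, HBGI, LBGI, MAGE (4) and CONGA_n (1) give 10 glucose indices, or 9. The fear survey makes 11, or 10.

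**Number of tests.** The plan does not fix this. Three readings for 10 glucose indices:

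| Reading | Tests | Expected false positives (tests x 0.05) | If independent, 1 - 0.95^tests |
|---|---|---|---|
| A. One three-arm test per index, averaged over pregnancy | 10 | 0.5 | 40.1% |
| B. Three-arm test per index in each trimester | 10 x 3 = 30 | 1.5 | 78.5% |
| C. Three arm pairs per index in each trimester | 10 x 3 x 3 = 90 | 4.5 | 99.0% |

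**Allowing for correlation.** The indices overlap heavily, so independence overstates the risk. Null trials were simulated with 10 equally correlated indices, arms of 10/20/40 (the anticipated numbers plus up to 30 retrospective controls) and a between-trimester correlation of 0.6. Both correlations are assumptions. Chance of at least one p < 0.05:

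| Between-index correlation | A | B | C |
|---|---|---|---|
| 0.3 | 36% | 66% | 93% |
| 0.8 | 18% | 38% | 67% |

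At a correlation of 0.5, reading A gives about 30% and reading C about 87%. Arms of 8/16/8 give nearly the same results.

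**Cross-check with simulated SMBG profiles.** Seven points a day for seven days in each of three trimesters were generated under no effect. The 10 indices were computed from them and one independent fear score was added. Assumed inputs: woman-level mean 130 mg/dL (SD 18), coefficient of variation about 0.38, target 63-140 mg/dL and between-trimester correlation 0.5 to 0.8. The mean absolute correlation between indices was about 0.63. The chance of at least one p < 0.05 was 21-23% for 11 three-arm tests in one trimester, 43-49% for 33 such tests over three trimesters, and 74-81% for 99 pairwise tests.

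**After the change.** Two named tests at 0.05 each would give 1 - 0.95^2 = 9.75% if independent. At 0.025 each the risk is at most 5%.

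**Power cost.** Take 20 v 10 women and an assumed standardized difference of 0.8. The noncentrality is 0.8 x sqrt(20 x 10 / 30) = 2.07 on 28 degrees of freedom. Two-sided power is 51% at 0.05 and 39% at 0.025. With 16 v 8 women it is 42% and 31%.

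**The case against.** The strongest objection is that the plan never prescribes the 90-test grid. It specifies linear mixed models for the glucose and fear endpoints, and names t-tests only for the follower alert and intervention rates. This stands. A reader might infer that a false positive is likely or even expected, but the documents do not support that as a general statement. It is true of reading C and of reading B at lower correlations. Under reading A the chance stays below 40%, before the within-woman and Share-interaction tests that the plan also describes.

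Two other strong inferences fail. A count of at least 11 primary measures is not a floor, because reading mean and SD as one summary gives 10. The primary-outcome list in the opening summary is also shorter than the one in the analysis plan. Nor does each hypothesis imply a single contrast: the CGM hypothesis names several outcomes, and the Share hypothesis names two outcomes and two comparators. Any choice of deciding contrast is therefore a selection that the sponsor must make.

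The last objection is that this is a non-randomized pilot without formal power, so splitting alpha is excessive. That limits how serious the point is and makes an exploratory label an acceptable remedy. It does not answer the point, because the plan keeps a significance rule and gives no p-value an exploratory label. Low power does not reduce false positives.

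**Conclusion.** The concern holds in this form: the plan declares a significance rule over many primary measures and does not say which result decides either endpoint. The risk of at least one false-positive glucose result is about 18-36%, 38-66% or 67-93% on the three readings, or roughly 3.6 to 18.6 times the nominal 5% (18/5 and 93/5). No single percentage can be attached to the plan, and that indeterminacy is part of the defect.

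The ranges rest on assumed between-index correlations of 0.3 to 0.8, a between-trimester correlation of 0.6, two-sided tests (the plan does not state sidedness) and no true difference between arms, including none from women choosing their own arm. They leave out the fear survey, the within-woman and Share-interaction tests, and duplicate SMBG and CGM versions of an index, all of which push the risk up. This should be corrected, but it does not invalidate the study.

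**What to change.** In the Statistical Analysis Plan, and to match in the primary outcomes of the opening summary and the Primary Objectives, name one measure, one contrast and one mixed-model estimand per primary endpoint. The choice is the sponsor's. One pair that fits the stated hypotheses is:

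- **Glucose:** percent of SMBG readings below one pre-stated target limit, Groups 1 and 2 combined v Group 3, averaged over the second and third trimesters. The limit must be stated for SMBG, because the listed cut-offs are given for CGM data. The plan should also say which readings the retrospective controls contribute: the Control Arm section gives them meter downloads and does not mention the 7-point profiles.
- **Fear:** total survey score, Group 2 v Group 1, over the same period. This contrast avoids Group 3, whose retrospective members have no fear data.

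Test the two with Holm, or at 0.025 each. Report every other index, arm pair and time point as an estimate with a 95% confidence interval, labelled exploratory, with no claim of significance. Naming the period matters: without it, each test could still be repeated by trimester or month, and Holm over two tests would not control that.

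The minimum alternative is to label all p-values exploratory and delete the p < 0.05 rule.

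The cost is wording in three places and no new data collection. The named tests face a stricter threshold (power 51% to 39% in the example above at 0.025, with a smaller loss under Holm), and the remaining results lose the label of significance.

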Appendix A

The Dexcom G4 Platinum® CGM system should be used:
 
★ For measuring interstitial glucose levels from the sensor tip which is inserted into the skin of the abdomen or forearm.★ With calibration with measurements of blood sugar levels from fresh capillary whole blood samples taken from the fingertip, palm (at the base of the thumb), or forearm. 
For use at home by persons with diabetes, or in a clinical setting by healthcare professionals, as an aid to monitor the effectiveness of diabetes control.
	
About the Share™ technology
 
★ Remote monitoring capacity: Bluetooth® Low Energy technology.★ Compatibility with: iPhone versions 4S through 6 Plus, iPod touch 5th Gen, iPad versions 3 and 4, iPad Air and Air 2, iPad Mini versions 1 through 3.★ Apps: Dexcom Share and Dexcom Follow both require internet connectivity★ Number of followers allowed: 5.★ Information sharing: Applies when the app is running in the foreground or background, as long as the app is open.★ Access to trend graph and notification settings: Applies when the Sharer sets access to the follower, Sharer can change access to the trend graph, Follower can modify the notification settings.
---------------------------------------------------------------------------------------------------------------------------------------------------------------------------------------------------------------------------------------------------------------------------------------------------------------------------------------------------------------------------------------------------------------------------------------------------------------------------------------------------------------------------------------------------------------------------------------------------	----------------------------------------------------------------------------------------------------------------------------------------------------------------------------------------------------------------------------------------------------------------------------------------------------------------------------------------------------------------------------------------------------------------------------------------------------------------------------------------------------------------------------------------------------------------------------------------------------------------------------------------------------------------------------------------------------------------------------------------------------------------------------------------------------------------------------------------------------

Appendix B

Baseline Participant Questionnaire

Subject ID: _____ Study Visit: (dd/mmm/yyyy) : _____ / _____ / _____

DEMOGRAPHIC INFORMATION

Date of Birth _____
(dd/mmm/yyyy)

Ethnicity

- Asian/Oriental
- African American
- Caucasian
- Hispanic or Latino
- Other

If other, specify _____

Education

- Grade school
- High School/GED
- Some College
- Associates degree
- Bachelor's Degree
- Master's degree
- Other

If other, specify _____

Marital Status

- Single
- Married
- Widowed
- Other

If other, specify _____

DIABETES HISTORY

Duration of Diabetes: _____

Immediate family history of diabetes? Yes No

Method of Insulin delivery:

- MDI
- Pump Therapy
- VGO Insulin Therapy

Type and Average Dose of Insulin Used:

Basal: _____ Dose _____

Bolus: _____ Dose _____

Other Diabetes medications? _____

If yes, specify _____

CGM Use: Current CGM user If yes, duration of previous use _____
 Past CGM user
 Never used CGM

DIABETIC COMPLICATIONS

Diabetic Retinopathy? Yes No Unknown

Diabetic sensory or motor neuropathy? Yes No Unknown

Diabetic autonomic neuropathy? Yes No Unknown

Diabetic nephropathy? (including micro-albuminuria) Yes No Unknown

If yes, please specify the most recent event diagnosed at the time of patient inclusion:

Impaired renal function (estimated GFR by MDRD below 60mL/min)

Micro-albuminuria (30-299mcg per mg creatinine)

Overt proteinuria (equal to or above 300 mcg per mg creatinine)

High Cholesterol? Yes No Unknown

High Blood Pressure? Yes No Unknown

PRE-EXISTING CONDITIONS

Does the subject have any pre-existing conditions? Yes No

If yes, list below

CONCOMITANT THERAPY

Is the subject taking any medications other than insulin? Yes No If yes, list below

PREVIOUS OBSTETRIC HISTORY

Past pregnancy? Yes No
If no, skip to next section.

Fill out information for each pregnancy. If there are more than 4 pregnancies, continue on another sheet.

First Pregnancy

Outcome Date _____
(dd/mmm/yyyy)

Delivery type:

Vaginal 	If yes: Spontaneous 	Induced 	Breech 	Vacuum 	Forceps 
VBAC 	If yes: Spontaneous 	Induced 			
Cesarean Section 	If yes: Low Transverse 	Low Vertical 	Classical 	Unspecified 	
Abortion 	If yes: Spontaneous 	Therapeutic 			
Tubal/ectopic 					

Gestational Age _____ Birth Weight _____

Preterm labor during pregnancy? Yes No

Child is still living? Yes No

Pregnancy complications? Yes No

If yes, check all that apply:

Pregnancy-induced hypertension 	Hypoglycemic seizure 
Eclampsia/Pre-eclampsia 	Diabetic Ketoacidosis 
Large for gestational age baby 	Progression of diabetic complication(s) 
Small for gestational age baby 	Other  Specify _____

Labor complications? Yes No

If yes, check all that apply:

Fetal Intolerance 	Anesthetic Complications 
Eclampsia/Pre-eclampsia 	Dysfunctional Labor 
Seizures during Labor 	Cephalopelvic Disproportion 
Aburptio Placenta 	Placenta Previa 
Shoulder Dystocia 	Excessive Bleeding 
Failure to Progress in First State 	Failure to Progress in Second State 
Neonatal Hypoglycemia 	Other  Specify _____

Second Pregnancy

Outcome Date _____
(dd/mmm/yyyy)

Delivery type:

Vaginal 	If yes: Spontaneous 	Induced 	Breech 	Vacuum 	Forceps 
VBAC 	If yes: Spontaneous 	Induced 			
Cesarean Section 	If yes: Low Transverse 	Low Vertical 	Classical 	Unspecified 	
Abortion 	If yes: Spontaneous 	Therapeutic 			
Tubal/ectopic 					

Gestational Age _____ Birth Weight _____

Preterm labor during pregnancy? Yes No

Child is still living? Yes No

Pregnancy complications?

Yes No

If yes, check all that apply:

Pregnancy-induced hypertension
Eclampsia/Pre-eclampsia
Large for gestational age baby
Small for gestational age baby

Hypoglycemic seizure

Diabetic Ketoacidosis

Progression of diabetic complication(s)

Other Specify _____

Labor complications?

Yes No

If yes, check all that apply:

Fetal Intolerance
Eclampsia/Pre-eclampsia
Seizures during Labor
Aburptio Placenta
Shoulder Dystocia
Failure to Progress in First State
Neonatal Hypoglycemia

Anesthetic Complications

Dysfunctional Labor

Cephalopelvic Disproportion

Placenta Previa

Excessive Bleeding

Failure to Progress in Second State

Other Specify _____

Third Pregnancy

Outcome Date _____
(dd/mmm/yyyy)

Delivery type:

Vaginal If yes: Spontaneous Induced Breech Vacuum Forceps
VBAC If yes: Spontaneous Induced
Cesarean Section If yes: Low Transverse Low Vertical Classical Unspecified
Abortion If yes: Spontaneous Therapeutic
Tubal/ectopic

Gestational Age _____

Birth Weight _____

Preterm labor during pregnancy?

Yes No

Child is still living?

Yes No

Pregnancy complications?

Yes No

If yes, check all that apply:

Pregnancy-induced hypertension
Eclampsia/Pre-eclampsia
Large for gestational age baby
Small for gestational age baby

Hypoglycemic seizure

Diabetic Ketoacidosis

Progression of diabetic complication(s)

Other Specify _____

Labor complications?

Yes No

If yes, check all that apply:

Fetal Intolerance
Eclampsia/Pre-eclampsia
Seizures during Labor
Aburptio Placenta
Shoulder Dystocia
Failure to Progress in First State
Neonatal Hypoglycemia

Anesthetic Complications

Dysfunctional Labor

Cephalopelvic Disproportion

Placenta Previa

Excessive Bleeding

Failure to Progress in Second State

Other Specify _____

Fourth Pregnancy

Outcome Date _____
(dd/mmm/yyyy)

Delivery type:

Vaginal 	If yes: Spontaneous 	Induced 	Breech 	Vacuum 	Forceps 
VBAC 	If yes: Spontaneous 	Induced 			
Cesarean Section 	If yes: Low Transverse 	Low Vertical 	Classical 	Unspecified 	
Abortion 	If yes: Spontaneous 	Therapeutic 			
Tubal/ectopic 					

Gestational Age _____ Birth Weight _____

Preterm labor during pregnancy? Yes No

Child is still living? Yes No

Pregnancy complications? Yes No

If yes, check all that apply:

Pregnancy-induced hypertension 	Hypoglycemic seizure 
Eclampsia/Pre-eclampsia 	Diabetic Ketoacidosis 
Large for gestational age baby 	Progression of diabetic complication(s) 
Small for gestational age baby 	Other  Specify _____

Labor complications? Yes No

If yes, check all that apply:

Fetal Intolerance 	Anesthetic Complications 
Eclampsia/Pre-eclampsia 	Dysfunctional Labor 
Seizures during Labor 	Cephalopelvic Disproportion 
Aburptio Placenta 	Placenta Previa 
Shoulder Dystocia 	Excessive Bleeding 
Failure to Progress in First State 	Failure to Progress in Second State 
Neonatal Hypoglycemia 	Other  Specify _____

ALCOHOL AND TOBACCO CONSUMPTION HABITS

Past cigarette use? Yes No

Current cigarette use? Yes No

If yes, usage duration _____

Alcohol use:	Never 	At least weekly 
	Occasionally (less than monthly) 	At least daily 
	At least monthly 	

How many standard drinks* containing alcohol does subject have on a typical day when drinking?

1 or 2

Greater than 2

*standard drink: 1 pint/bottle of beer, 1 glass of wine, 1 shot of hard liquor

